3.5 Indicators of a Difficult IUD Insertion

- *Cervical dilation*: indicator variable (0 = No, 1 = Yes) for whether cervical dilation was used during the IUD insertion procedure
- *Ultrasound guidance*: indicator variable (0 = No, 1 = Yes) for use of ultrasound guidance during placement of the IUD on the day of the IUD insertion
- *Paracervical block*: indicator variable (0 = No, 1 = Yes) for whether the patient received a paracervical block during the IUD insertion procedure
- *Provider note indicating a difficult insertion or complicated procedure*: indicator variable (0 = No, 1 = Yes) for whether the patient record includes a notation from the provider regarding a difficult insertion or complicated procedure
- *Use of misoprostol*: indicator variable (0 = No, 1 = Yes) for whether the patient received misoprostol during the 7 days before or on the date of the IUD insertion procedure

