- **Cervical dilation** will be identified on the day of the IUD insertion and will be classified as yes or no. If there is no information in the record that cervical dilation was done, then the classification will be “no.”
- **Ultrasound guidance** for the placement of the IUD will be identified on the day of the IUD insertion and will be classified as yes or no. If there is no information in the record that ultrasound guidance was used, then the classification will be “no.”
- **Paracervical block:** indicator variable (0 = No, 1 = Yes) for whether the patient received a paracervical block during the IUD insertion procedure. If there is no information in the record that a paracervical block was used, then the classification will be “no.”
- **Provider note indicating a difficult insertion or complicated procedure:** indicator variable (0 = No, 1 = Yes) for whether the patient record includes a notation from the provider regarding a difficult insertion or complicated procedure. If there is no notation of this in the record, then the classification will be “no.”
- **Use of misoprostol:** indicator variable (0 = No, 1 = Yes) for whether the patient received misoprostol during the 7 days before the IUD insertion procedure.

Provider-related characteristics, where available (i.e., KPNC, KPSC, KPWA)

- **Provider number of IUD insertions in the previous year:** number of IUD insertions the provider performed in the previous year.
- **Provider annualized number of IUD insertions in the previous year:** provider number of IUD insertions in previous year divided by the number of months provider was employed by health care system represented in data source.
- **Categorical indicator for number of IUD insertions in the previous year:** 0 = fewer than 50 IUD insertions in the previous year, 1 = 50 or more IUD insertions in the previous year.
- **Provider length of employment in the previous year:** continuous variable of the number of days employed within the health care system in the past year.

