Patients will be followed from the time of IUD insertion until the first occurrence of any of the following: uterine perforation, IUD expulsion, IUD removal, indication of IUD reinsertion, indication of new pregnancy, hysterectomy, death, expiration of IUD, disenrollment from the database, or end of the study period. All person-time at risk that meets these criteria will be included, and there will be no requirement for minimum or maximum follow-up time. All IUD insertions occurring with at least 12 months of enrollment before the insertion that are noted within the data sources will be included in the study. The index date will be captured for each insertion, and baseline data will be collected for each index date (Figure 2). The main analyses for the study will

assess only the first observed IUD insertion for each woman in the database. Secondary analyses will be conducted assessing subsequent insertions (i.e., not the first IUD insertion), as recorded in the database. The sequential number of each insertion, as captured in the data for each woman, will be collected and included as a baseline covariate within these secondary analyses.

Figure 2. Covariate data collection around index date

Exposures of postpartum status (based on pregnancy delivery date), breastfeeding status, IUD type, and menorrhagia (as a proxy for indication of use) will be assessed as of the index date of IUD insertion. Outcomes of uterine perforation and IUD expulsion will be assessed beginning on the index date. Baseline data—such as patient demographics, patient characteristics (e.g., personal history of gynecologic conditions such as endometriosis), procedure characteristics, medications, and comorbid conditions (e.g., diabetes)—will be collected from all time in the database before the index date (which will be defined as the day of IUD insertion) and on the index date (Figure 2). Provider characteristics, procedure-related characteristics, and indicators of a difficult insertion will be assessed on the index date (i.e., on the same date or within the same encounter as the index date). The variables to be obtained from each research site are provided in Sections 3.1 through 3.8.

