4.6 Definition of Derived Variables and Subgroups

The variables described in Table 1 will be derived by RTI-HS using the data provided by the four research sites. Since the unit of observation in the data provided by the research partners will be an IUD insertion, these variables will be calculated for each insertion and included in the final dataset. If a woman has more than one eligible insertion in the dataset, the variables will be derived for each insertion using data relevant to that insertion.

Table 1. Definition of Derived Variables

Variable	Definition ^a
Baseline covariates	
IUD insertion count	The number of eligible IUD insertions for the woman as of the index date (including the index insertion). IUD insertion count increases by 1 each time a new index date is identified for the woman
Initial IUD insertion	Indicator variable: If IUD insertion count = 1 then initial IUD insertion = 1 If IUD insertion count > 1 then initial IUD insertion = 0
Difficult insertion	Indicator variable: 1 = Yes if any of the following occur on the index date (or in 7 days before index date for misoprostol): cervical dilation, ultrasound guidance, paracervical block, provider note, use of misoprostol 0 = No if none of the above indicators of difficult insertion are found on the index date
Age tertile	Categorical variable for age based on tertiles (or closest integer cut point [i.e., in years]) for all ages at all first index dates observed within the data
Duration of look-back period	Derived number of days, starting on the date of start of enrollment or first clinical encounter in the EHR database and ending on the index date Duration of look-back period is calculated for each index date
Categorical indicator for provider number of insertions in previous year	Indicator variable: 0 = fewer than 50 provider number of IUD insertions in the 365 days prior to and on the index date, 1 = 50 or more provider number of IUD insertions in the 365 days prior to and on the index date
Provider annualized number of insertions in previous year	Provider number of IUD insertions in previous year divided by provider length of employment in previous year , multiplied by 365

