Concomitant gynecological procedure	Indicator variable: 1 = Yes if any of the following procedures occurred on the index date: abortion, aspiration and curettage, dilation and curettage, excision/biopsy of cervix or uterus, ablation, colposcopy and other cervical procedures, hysteroscopy, laminaria, laparoscopy, lysis adhesions, myomectomy, nerve procedure, salpingectomy/oophorectomy 0 = No if none of the above procedures occurred on the index date
Exposures	
Postpartum number of days	Number of person-days, starting on the most recent pregnancy delivery date prior to or on the index date and ending on the index date . There will be a derived postpartum number of days associated with each insertion for each woman. This variable will range from 0 to 365 days and will be missing if the most recent pregnancy delivery date is not recorded or is more than 365 days before the index date .
Postpartum—14-week, dichotomous	Indicator variable: * If postpartum number of days ≤ 98, then postpartum—14-week, dichotomous = 1 * If postpartum number of days > 98 or missing, then postpartum—14-week, dichotomous = 0

Variable	Definition ^a
Postpartum—36-week, dichotomous	Indicator variable: * If postpartum number of days ≤ 252 , then postpartum—36-week, dichotomous = 1 * If postpartum number of days > 252 or missing, then postpartum—36-week, dichotomous = 0
Postpartum—categorical	Categorical variable: * If postpartum number of days ≤ 42 , then postpartum—categorical = 1 (6 weeks or less) * If postpartum number of days > 42 and ≤ 98 , then postpartum—categorical = 2 (> 6 to ≤ 14 weeks) * If postpartum number of days > 98 and ≤ 365 , then postpartum—categorical = 3 (> 14 to ≤ 52 weeks) * If postpartum number of days > 365 or missing, then postpartum—categorical = 0 (> 52 weeks or no delivery)
Outcomes	
Person-time at risk (days, i.e., time to event/censor)	Number of person-days, starting on the index date of IUD insertion and ending on the earliest of date uterine perforation confirmed , date IUD expulsion confirmed , or censoring date . A derived number for person-time at risk will be associated with each IUD insertion for each woman.
Uterine perforation event indicator	Indicator variable: 0 = No date of uterine perforation confirmed during the person-time at risk 1 = Yes, date of uterine perforation confirmed during the person-time at risk

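### For insertions on postpartum days 0–7 the 7-day misoprostol window contains the delivery, so delivery-related misoprostol can be counted as a difficult insertion in the ≤ 6 week row of objective 13

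*SAP*

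**What the plan says.** **The misoprostol item.** SAP 3.5 records "whether the patient received misoprostol during the 7 days before or on the date of the IUD insertion procedure". Protocol 9.3.1 has nearly the same window, "whether the patient received misoprostol during the 7 days before the IUD insertion procedure". Neither asks why the drug was given or whether a delivery lies in the window.

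**The composite.** SAP 4.6, Table 1 defines Difficult insertion as "1 = Yes if any of the following occur on the index date (or in 7 days before index date for misoprostol"), followed by the five indicators. Any one of them is enough.

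**Who is eligible.** For postpartum number of days, Table 1 states: "This variable will range from 0 to 365 days". Days 0–42 form the ≤ 6 week category, with no separate handling of the first week.

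**Where the indicators are used.** SAP 6.3.2 and Table Layout 9 show each indicator and 'Any' by postpartum category (objective 13, Tables 13.1–13.5). SAP 4.1.5 takes propensity score candidates from SAP Sections 3 and 4.6, and Table 1 lists Difficult insertion among the baseline covariates.

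**The procedural indicators.** SAP 3.5 ties cervical dilation to the insertion ("whether cervical dilation was used during the IUD insertion procedure") and defines the ultrasound item "for use of ultrasound guidance during placement of the IUD on the day of the IUD insertion". Paracervical block is likewise tied to the insertion procedure. Two wordings are looser. Protocol 9.3.1 says that dilation "will be identified on the day of the IUD insertion and will be classified as yes or no". SAP Section 3 has the difficulty indicators "assessed on the index date (i.e., on the same date or within the same encounter as the index date").

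**The concern.** Where there has been no recent delivery, misoprostol in the week before an insertion can reasonably be read as preparation for it. When the insertion follows a delivery by 0–7 days, the same record may belong to the delivery. The rule cannot tell the two apart, and one such record turns the composite to Yes.

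The error runs one way, upward, and it falls in the ≤ 6 week row. That row matters: Protocol Section 7 says that immediate postpartum placement is more common in the US than in Europe, and that the FDA is particularly interested in time from delivery to placement. A reader of Tables 13.1–13.5 could take an excess there as evidence that early insertions are harder.

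There is a second, conditional route. If the misoprostol item or the composite enters a postpartum-timing propensity score model, weighting balances a flag that may mean delivery care in early-postpartum women against a flag that may mean real difficulty in women of the referent group.

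**Working it through.** **1. The plan's denominator.** Protocol 9.5 expects 225,000 first insertions, allocated 5:20:5:70. 225,000 × 5/100 = 11,250, which matches the ≤ 6 week row of Protocol Table 5. The documents state no prevalence of difficult insertion, so no stated result is contested.

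**2. The overlap in days.** The window runs from 7 days before insertion to the insertion day. The delivery date lies inside it when postpartum number of days is 0, 1, …, 7. That is 8 of the 43 possible days (0–42) in the category: 8/43 = 18.6% if insertions were spread evenly. For indicators without a 7-day window, the dates coincide on day 0 only: 1/43 = 2.3% on the same footing, or longer if a shared encounter counts.

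**3. Size.** Let s be the share of ≤ 6 week insertions on days 0–7, q the share of those with delivery-related misoprostol in the window, and p the true prevalence of any indicator. None of the three is in the documents; all are assumed. Taking q as independent of true difficulty:

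- false misoprostol flags = 11,250 × s × q
- observed composite = p + (1 − p) × s × q
- rise among all users = 0.05 × (1 − p) × s × q, because the group is 5% of insertions

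With p = 5%:

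| s | q | False misoprostol flags | Composite reads | Rise, ≤ 6 weeks (points) | Rise, all users (points) |
|---|---|---|---|---|---|
| any | 0 | 0 | 5.0% | 0 | 0 |
| 5% | 15% | 84 | 5.7% | 0.71 | 0.04 |
| 5% | 30% | 169 | 6.4% | 1.43 | 0.07 |
| 20% | 15% | 338 | 7.9% | 2.85 | 0.14 |
| 20% | 30% | 675 | 10.7% | 5.70 | 0.29 |
| 40% | 30% | 1,350 | 16.4% | 11.40 | 0.57 |

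Example: 0.05 + 0.95 × 0.20 × 0.30 = 0.107. Some flagged women would be Yes anyway, so at s = 20% the composite gains 0.95 × 338 to 0.95 × 675, or about 321–641 women. The assumed p matters little to the rise: at s = 20% and q = 15–30%, p = 2% reads 4.9–7.9% and p = 10% reads 12.7–15.4%.

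**4. Route into the adjusted analyses.** Under SAP 4.1.5 a covariate enters if its crude hazard ratio exceeds 1.11 or is below 0.90, or if adjusting for it changes the exposure hazard ratio by at least 10%. The first criterion needs no significance test, so entry is possible. Whether it happens, and with what bias, cannot be computed from the documents.

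**The case against.** **The same-day indicators.** A reader might infer that all the indicators overlap the delivery across days 0–7. The documents do not support this. Only misoprostol has a 7-day window, and SAP 3.5 ties dilation, ultrasound and paracervical block to the IUD procedure. For these, only the calendar-day wording for dilation in Protocol 9.3.1 and the same-encounter wording in SAP Section 3 need to be reconciled with SAP 3.5.

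**Inflation as a fact.** A reader might also conclude that the ≤ 6 week prevalence is inflated. Neither document says that misoprostol is used around delivery, how often, or how many insertions fall on days 0–7. What is shown is a rule that would count such records. This objection stands, and the wording here is limited accordingly.

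**Small and visible.** Objective 13 is descriptive and concerns all users, whose figure barely moves. Layout 9 gives misoprostol its own column, so an excess would be seen. That is fair, but the column would not show whether the excess came from deliveries or insertions, and 'Any' would still carry it.

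**Abortion.** Misoprostol given for a concomitant abortion is caught too. Unless there was also a recorded delivery within 52 weeks, that woman is in the referent category, so this raises the referent row and partly offsets the contrast. It adds to the problem of meaning, not to the ≤ 6 week excess.

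**Definitions held elsewhere.** SAP Section 4 refers to a Data Structure Template with operational definitions, which may attribute misoprostol orders and is not available here. The same section says that derived variables are to be detailed in the SAP, and the composite is one. Its definition there has no exclusion.

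**Conclusion.** The point holds for misoprostol and for the composite that it drives. As written, the rule counts delivery-related misoprostol as a difficult insertion when insertion is on postpartum days 0–7, and can raise two columns of the ≤ 6 week row in objective 13. The rise is 2.85–5.70 points if 20% of that group is inserted on days 0–7 with 15–30% peripartum use, 0.71–1.43 points if 5% is, and nil without such use. All of these rest on assumed shares and an assumed true prevalence of 5%.

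A reader might go further and infer that the adjusted hazard ratios of primary objective 2 are biased. The documents establish only that the two items are candidates; selection depends on the data, and no bias has been sized. No sample size or power figure changes.

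**What to change.** Use only data already held: the derived postpartum number of days and the abortion indicator (SAP 3.4).

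1. **SAP Table 1, Difficult insertion.** Do not let misoprostol alone set the composite to Yes when postpartum number of days is 0–7 or an abortion is recorded on the index date. The other indicators still count.
2. **Tables 13.1–13.5 (Layout 9).** Split the ≤ 6 week row into days 0–7 and days 8–42, and present 'Any' with and without misoprostol.
3. **Postpartum-timing propensity score models.** In models 2 and 6 of SAP 9.3, and so in models 11 and 14, which inherit their covariates, use the composite without misoprostol and omit the misoprostol item. Settle this in advance, because covariate selection is not blinded to outcome.
4. **Wording.** Reconcile Protocol 9.3.1 (dilation by calendar day) and SAP Section 3 (same encounter) with SAP 3.5.

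The cost is one conditional line of code, one extra table row and one extra column. Under step 1 the composite becomes No, not missing, so the complete-case rule in SAP 4.3 drops no insertions. A rule based on order indication or closure of the delivery encounter would be more exact, but needs variables not listed in SAP 3.1–3.8.

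There are two limits. A few truly difficult insertions soon after delivery, identified only by misoprostol, would not be counted. The abortion flag covers the index date only and may be missing at the Regenstrief site.

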3.6 Provider-Related Characteristics (Not Captured in RI Data)

- *Provider number of IUD insertions in the previous year*: number of IUD insertions the provider performed in the previous year as of the index date
- *Provider length of employment in the previous year*: continuous variable of the number of days employed within the health care system in the past year as of the index date

3.7 Start and Stop Dates¹

- *IUD insertion date* is the date on which IUD insertion is documented
- *Beginning date of study period*: the first date EHR data are available from the data source for this study (KPNC, KPSC, and KPWA) or the date when Mirena was launched (RI)
- *End date of study period*: the last date on which EHR data are available from the data source for this study
- *Date of start of enrollment* (KPNC, KPSC, and KPWA only) is the earliest date of enrollment in the database for the woman (will be used to calculate look-back period)
- *Date of first clinical encounter* (RI only) is the earliest in-person visit in the database for the woman (will be used to calculate look-back period)
- *Date of disenrollment from the database* (KPNC, KPSC, and KPWA only) is the date, after the index date, on which the woman was no longer enrolled in an eligible insurance plan (one gap of ≤ 31 days per year will be allowed)
- *Date of last clinical encounter in database* (RI only) is the last date on which a woman had an in-person encounter that was recorded in the database

¹ Note that the actual dates will remain at each data source research partner. The dates may be offset for each patient as an additional data protection measure before transfer of data to RTI-HS.

- *Censoring date* is the earliest of the following dates: date of removal of IUD, date of a subsequent IUD reinsertion, date of start of new pregnancy, hysterectomy date, date of bilateral oophorectomy or other type of sterilization, expiration of IUD, death date, date of disenrollment from database (KPNC, KPSC, and KPWA only) or last clinical encounter (RI only), and end date of study period

3.8 Other Parameters

- *Database*: categorical variable of the four data sources included in the study
- *Live birth at most recent delivery*: indicator variable (0 = No, 1 = Yes) for whether the patient had a pregnancy ending in live birth within the 52 weeks before the index date
- *Date of start of most recent (continuous) enrollment* (KPNC, KPSC, and KPWA only) is the date, prior to the index date, on which the woman started enrollment in an eligible insurance plan (one gap of ≤ 31 days per year will be allowed)

4 General Statistical Considerations

All issues concerning patient eligibility, data consistency checks, permissible data modifications, and coding of medical terms and medication will be documented and maintained by research partners following the Data Structure Template (a central document including operational definitions developed by RTI Health Solutions (RTI-HS) and the data source research partners) and the Work Practice Document for quality control. All statistical issues including derived variables are to be detailed in this statistical analysis plan. Determination of sample size was detailed in the study protocol.

4.1 General Principles

The statistical evaluation will be performed by using the software package SAS version 9.4 or higher (SAS Institute Inc., Cary, NC, USA), except when noted otherwise.

The analysis conducted at RTI-HS will follow the relevant RTI-HS standard operating procedures. Programs, logs, and output will be reviewed for accuracy according to the standard operating procedures for programming and quality control. In addition to table creation, some variables will be derived by RTI-HS from the data provided by the research sites; these derived variables are described in Section 4.6. Variables listed in Section 3 will be provided by sites from their databases via use of operational definitions defined by the research team. For data analyses at each site, the standard operating procedures for the site will be used to ensure data quality and security.

4.1.1 Descriptive Analyses

Descriptive analysis of the data will be performed using summary statistics for categorical and quantitative (continuous) data. Continuous data will be described by the number of nonmissing values, median, mean, standard deviation, minimum, and maximum, as well as lower and upper quartiles. Frequency tables will be generated for categorical data. Selected continuous variables will be categorized in a clinically meaningful way or by tertiles of the distribution.

4.1.2 Crude Incidence Rates

Crude incidence rates (I) will be calculated as the number of incident outcomes (E) occurring during the person-time at risk divided by the total person-years at risk (Y).

$$I = \frac{E}{Y}$$

The exact confidence intervals (CIs) will be calculated using the relationship between the Poisson distribution and chi-square distribution as described in Dobson et al. (1991). The lower and upper bounds (LB and UB) of the 95% CI will be calculated as follows:

$$I_{LB} = \max\left(0, \left(\frac{X_{2E,0.025}^2}{2}\right) / Y\right), I_{UB} = \left(\frac{X_{2(E+1),0.975}^2}{2}\right) / Y$$

where $X_{d,\alpha}^2$ represents the α th percentile of the chi-square distribution with d degree of freedom.

Crude incidence rates will be reported as point estimates (number of cases per 1,000 person-years) and 95% CIs.

